## 910 ANNEX V – Subjective Perception of Effort Scale

0	Nenhum esforço (Repouso)
1	Muito Fraco
2	Fraco
3	Moderado
4	Um Pouco Forte
5	Forte
6	
7	Muito Forte
8	
9	
10	Esforço máximo

911

912

Carga Interna = Valor apontado de PSE x minutos da sessão de treino

913

914

915

## 888 ANNEX VI – Brunel Mood Scale (BRUMS)

**A Escala de Humor de Brunel (BRUMS)**

Abaixo está uma lista de palavras que descrevem sentimentos. Por favor, leia tudo atenciosamente. Em seguida assinale, em cada linha, o quadrado que melhor descreve **COMO VOCÊ SE SENTE AGORA**. Tenha certeza de sua resposta para cada questão, antes de assinalar.

**Escala:**

0 = nada      1 = um pouco      2 = moderadamente  
 3 = bastante    4 = extremamente

	0	1	2	3	4
1. Apavorado					
2. Animado					
3. Confuso					
4. Esgotado					
5. Deprimido					
6. Desanimado					
7. Irritado					
8. Exausto					
9. Inseguro					
10. Sonolento					
11. Zangado					
12. Triste					
13. Ansioso					
14. Preocupado					
15. Com disposição					
16. Infeliz					
17. Desorientado					
18. Tenso					
19. Com raiva					
20. Com energia					
21. Cansado					
22. Mal-humorado					
23. Alerta					
24. Indeciso					

**PRESENTATION:**

Because triathlon is a sport that combines high intensity and long duration, it imposes significant physiological adaptation on the body. However, when the challenge exceeds the capacity for physiological adaptation, it is possible to observe the occurrence of various disorders in the athlete's health. In this sense, among the various factors that can help with this adaptation, it has been pointed out that the microbiota, which can be modulated by diet, age, medical treatments, lifestyle and physical exercise, can favor the maintenance of a healthy state. According to the literature, probiotics, prebiotics and synbiotics can benefit people in different ways. For example, by promoting immunoregulation, these elements can have an impact on preventing or reducing the frequency and/or intensity of upper airway symptoms, both in the general population and in athletes. However, it is worth noting that there are still no reports in the scientific literature on the effects of drinking fermented milk containing *Lacticaseibacillus paracasei* strain Shirota (LcS), a known probiotic agent, not only on the modulation of immune/inflammatory responses, but also on the manifestation of airway symptoms and mood in triathletes. Therefore, in this study, our aim will be to investigate, in general, the effect of daily intake of fermented milk containing 40 billion LcS in amateur triathletes, emphasizing that our primary endpoint will be to assess the occurrence of upper airway symptoms and the secondary endpoints will be to assess both systemic and upper airway immune/inflammatory responses, as well as mood states. To answer these endpoints, saliva, nasal swab and blood samples, as well as data on quality of life, upper airway symptom manifestation and mood states will be obtained on five different occasions: 30 days (1) and 24 hours before the competition (2), as well as immediately (3), 72 hours after the competition (4) and 24 hours after the competition (5).

**HYPOTHESIS:**

Supplementation with Lacticaseibacillus paracasei strain Shirota interferes with immune system modulation and performance in triathlon athletes.

**Research Objective:**

**PRIMARY OBJECTIVES**

To investigate the effect of daily intake of fermented milk containing 40 billion LcS on the occurrence of upper airway symptoms in amateur triathletes participating in this study, before and after an official triathlon competition.

**SECONDARY OBJECTIVES**

To evaluate the effect of the daily intake of fermented milk containing 40 billion LcS on the systemic and upper airway immune/inflammatory responses and also on the mood states of the amateur triathletes who took part in this study, before and after an official triathlon competition.

**Assessment of Risks and Benefits:**

Regarding the risks and benefits, the researcher declares:

**RISKS:**

The risks for the research volunteers will be minimal, both for the blood collection, because although it is a routine clinical procedure that is generally safe, there may be minor discomfort (pain) or hematoma at the puncture site, fainting or dizziness, and for the collection nasal cells through the nasal swab. In order to reduce these risks, the collection should always be carried out by trained professionals.

**Comments and Considerations on the Research:**

STUDY TYPE: double-blind, randomized, controlled trial with two parallel groups

LOCATION: Otorhinolaryngology Research Laboratory (ORL-LAB) . [name]

**PARTICIPANTS:**

- Inclusion criteria:

**EXCLUSION CRITERIA:**

- (1) reported intolerance to fermented milk;
- (2) are under any kind of pharmacological treatment;
- (3) report chronic rhinopathy;
- (4) have autoimmune diseases;
- (5) report the occurrence of recurrent non-airborne infections. In addition,
- (6) feeding during the study of foods containing Lactobacilli
- (7) if any data is missing from a volunteer, that participant will be excluded from the study

(for more information, see detailed design).

**Recommendations:**

RECOMMENDATION 1- It is the researcher's obligation to develop the research project in full compliance with the proposal submitted to the CEP. Changes and alterations to the protocol must be communicated in the form of an AMENDMENT through Plataforma Brasil.

Address:	[name]		
Neighborhood:	VILA CLEMENTINO	ZIP CODE:	04.021-
UF: SP	Municipalit	SAO PAULO	
Phone:	y:		E-mail [contact]

Continuation of Opinion: 7.349.261

**RECOMMENDATION 2-** From the date of approval, it will be necessary to send partial reports (every six months) and the final report (at the end of the study), by means of a NOTIFICATION on the Brazil Platform. Researchers must inform and justify to the CEP any need for temporary suspension or permanent suspension of the research. Incidents and adverse events must also be reported to CEP-Unifesp by means of a NOTIFICATION on the Brazil Platform.

**RECOMMENDATION 3-** Researchers should take all necessary precautions when collecting and storing data in order to guarantee the secrecy and confidentiality of the research participants' information. It is recommended to download the data collected to a local electronic device, deleting any data from virtual platforms or the cloud. The research protocol documents (files of forms, terms, data and samples) must be kept for at least 5 years after the end of the research.

**RESPONSE TO PENDING ISSUES**

---

**PENDENCY 1** - In relation to the timetable provided in the basic information form: we ask that the researchers check whether there is a need to change the start date for the "Recruitment and selection of volunteers" and subsequent stages, so that there is enough time between the responses and approval by the CEP/UNIFESP. We remind you that no study can begin before approval by CEP/UNIFESP (CNS Operational Standard 001 of 2013, item 3.3.f).

**ANSWER 1** The dates have been changed in the schedule presented in the Detailed Project and in the Brazil Platform.

**PENDENCY ATTENDED TO**

---

**PENDENCY 2** It is requested that the name of [name] (cited in field

Address:	[name]		
Neighborhood:	VILA CLEMENTINO	ZIP CODE:	04.021-
UF:SP	Municipalit	SAO PAULO	
Phone:	y:	E-mail: [contact]	
[name]			

Continuation of Opinion: 7.349.261

"Assistant", in the basic information form of Plataforma Brasil), be included on the front sheet (cover) of the detailed project.

ANSWER 2: The researcher's name has been added

PENDING CARRIED OUT

---

PENDENCY 3- Inform in the detailed project methodology and in the ICF the average time needed for participants to answer all the questionnaires. ANSWER 3: As requested, the average time needed to answer each questionnaire in this study has been added to both the main text of the study and the ICF. In this sense, it is worth mentioning that it will be necessary: - 5 to 7 minutes to answer the WURSS questionnaire, to check the occurrence of upper airway symptoms not only in this period, but also throughout the study period (Annex 1); - 10 to 12 minutes to answer the quality of life (Annex 2); - 5 to 8 minutes to answer the physical activity level questionnaire (Annex 3); - 5 to 7 minutes to answer the questionnaire with open questions about gastrointestinal problems. (Annex 04).

PENDENCY PARTIALLY FULFILLED CEP/UNIFESP ANALYSIS: The average time needed to answer the questionnaires was not added to the ICF.

Answer 3: The following text was added to the ICF: ¿It is worth mentioning that it will take 5 to 7 minutes to answer the WURSS questionnaire (to check the occurrence of upper airway symptoms), 10 to 12 minutes to answer the quality of life questionnaire, 5 to 8 minutes to answer the physical activity level questionnaire and, finally, 5 to 7 minutes to answer the questionnaire with open questions about gastrointestinal problems¿.

PENDENCY ATTENDED TO

---

PENDENCY 4- - According to the letter of referral, research participants linked to Hospital São Paulo and UNIFESP will not be involved. We therefore ask for clarification regarding the sending of the COEPE letter and the completion of the CEP registration form stating that UNIFESP outpatient clinics will be used. ANSWER 4: Vale

**Address:** [name]

**Neighborhood:** VILA CLEMENTINO

**UF:** SP

**Municipalit** SAO PAULO

**[contact]

**ZIP CODE:** 04.021-

**E-mail:** [contact]

Continuation of Opinion: 7.349.261

to clarify that for the development of this study proposal, clinical evaluation will be recommended with emphasis on otorhinolaryngological aspects. Therefore, in order to guarantee reliable data for each volunteer taking part in the study, we will use the outpatient facilities of the Department of Otorhinolaryngology and Head and Neck Surgery at UNIFESP exclusively to carry out this assessment. Finally, it is worth stating that no other UNIFESP sector/ambulatory will be used.

PENDENCY ATTENDED TO

---

PENDENCY 5- According to the letter of referral, in addition to the competition venues, participants will also be recruited from the Olympic Center and Unisa. Answer 5: With regard to this item, it is worth first clarifying that, as presented in the text of the research project, "In order to reach the number of volunteer groups (male and female), we will invite the athletes registered for the triathlon competition through direct contact with the athletes' advisors and also by sending the invitation to their social media." Therefore, recruitment will be carried out exclusively and directly by those responsible for developing the study and there will be no recruitment from the Olympic Center and Unisa. However, it is worth noting that the premises of the Olympic Center will be used to carry out the cardiorespiratory assessment, while the premises of UNISA will be used to collect, process and store the samples necessary for the development of this study, in addition to carrying certain laboratory assessments. 5a) It will be necessary to send a letter of consent/authorization from the person in charge of the sites regarding the research (one for each site). Answer 5a) As described above, since there will be no recruitment at the Olympic Center and Unisa, it is not necessary to send a letter of consent/authorization from the person in charge of the sites regarding the research. PENDENCY NOT FULFILLED CEP/UNIFESP ANALYSIS: Since the premises of the Olympic Center and UNISA will be used, it is necessary to send the letters of consent and authorization from those responsible for the sites.

Answer 5.a): Letters of consent have been attached to the Brazil Platform system

PENDENCY ATTENDED TO

PENDING 5.b) If recruitment is carried out through the media, social networks, posters, etc., the text of this recruitment must be sent to the CEP for analysis. This information

Address:	[name]		
Neighborhood:	VILA CLEMENTINO	ZIP CODE:	04.021-
UF: SP	Municipalit	SAO PAULO	
Phone:	y:	E-mail:	[contact]
[name]			

Continuation of Opinion: 7.349.261

should be included in the project methodology. **GUIDELINE:** Invitations to take part in the research should not be made using lists that allow the invitees to be identified or their contact details (e-mail, telephone, etc.) to be viewed by third parties. Any individual invitation sent by e-mail can only have one sender and one recipient, or be sent in the form of a hidden list. (C I R C U L A R OFFICE

NO. 2 / 2

0 2 1 / C O N E P / S E C N S / M S ,

d i s p o n i v e l e m :

[http://conselho.saude.gov.br/images/Oficio\\_Circular\\_2\\_24fev2021.pdf](http://conselho.saude.gov.br/images/Oficio_Circular_2_24fev2021.pdf)). Answer 5b) The text of the invitation letter to be sent to the athletes is shown in ANNEX 06. In addition, as requested, this information has been added to the main text of the research project, as shown below.

In order to reach the number of volunteer groups (male and female), we will invite the athletes registered for the triathlon competition through direct contact with the athletes' advisors and also by sending the invitation by e-mail or even to their social media. The text to be sent is shown in ANNEX 05 - PENDENCY PARTIALLY FULFILLED ANALYSIS CEP/UNIFESP: Correct the number of the annex referring to the letter of invitation (annex VII and not VI). Answer 5b) We have changed the numbering of the annex.

PENDENCY ATTENDED TO

---

PENDENCY 6 - We request that the methodology of the detailed project include the justification for the use of placebo, as CNS resolution 466/2012, item III.3.b., states that research must "have full justification, where appropriate, for the use of placebo, in terms of non-maleficence and methodological necessity, and the benefits, risks, difficulties and effectiveness of a new therapeutic method must be tested, comparing it with the best current prophylactic, diagnostic and therapeutic methods. This does not exclude the use of placebo or no treatment at all in studies in which there are no proven methods of prophylaxis, diagnosis or treatment.».

ANSWER 6: As requested, the use of placebo in this study is initially justified by the participant's acknowledged belief that the simple use of the bottle containing fermented milk will prevent the manifestation, as well as reduce the duration and airway symptoms associated with the triathlon competition. In addition, the placebo will be useful for understanding and isolating the biological effects, particularly those related immune/inflammatory aspects, considering the non-maleficence, beneficence and justice of

**Address:** [name]

**ZIP CODE:** 04.021-

**Neighborhood:** VILA CLEMENTINO

**UF:** SP **Municipalit:** SAO PAULO

**[contact]

**E-mail:** [contact]

Continuation of Opinion: 7.349.261

possible improvements in the manifestation of airway symptoms associated with triathlon competition. Finally, it is worth noting that the fermented milk containing SCL is an exclusive product of the company Yakult Honsha Co.,Ltd. and only it can supply the placebo for the development of this research project. The above text has been added to the main text of the research project, specifically in the sub-item "Ingestion of SCL" under "Materials and Methods".

PENDENCY ATTENDED TO

---

PENDENCY 7- Page 18 of the detailed project reads: *¿To ensure the development of a double-blind study, all vials used in the study will be kindly provided by YAKULT S/A Indústria e Comércio, Brazil.* We request that a letter from the company agreeing to provide the vials for research be attached to the Brazil platform.

ANSWER 7: In response to the request, the letter from YAKULT S/A Indústria e Comércio, Brazil stating that it will provide the vials has been attached to the Brazil Platform.

PENDENCY ATTENDED TO

---

PENDENCY 8- We would like to remind you that, according to Resolution 466/2012:III.3.d, if the treatment proves to be effective at the end of the study, the same treatment should be made available to the control group: please clarify and it will be necessary to include this information in the detailed project and in the ICF. (Resolution 466/2012:III.3.d, proposes.d, proposes: "Ensure that all participants at the end of the study, by the sponsor, have free and indefinite access to the best prophylactic, diagnostic and therapeutic methods that have been shown to be effective.").ICF: inform that if the treatment proves to be effective at the end of the study, the same treatment should be made available to the control group Answer 8: Regarding this item, it is worth clarifying that: 1) the research project will be carried out using a product (fermented milk containing LcS) which is not registered as a medicine but as a foodstuff, according to its registration with the Brazilian Ministry of Agriculture, Livestock and Supply, attached to the Brazil Platform; 2) the purpose of the study is not to evaluate the possible use of fermented milk containing LcS as a treatment for a specific disease or pathological process, but rather to evaluate the possible probiotic effect (immunomodulation) of this fermented milk in a specific context, which involves triathlon competition; 3)

Address:	[name]		
Neighborhood:	VILA CLEMENTINO	ZIP CODE:	04.021-
UF: SP	Municipalit	SAO PAULO	
Phone:	y:		E-mail [contact]
[name]			

Continuation of Opinion: 7.349.261

corroborating the item above, as presented in the research project, the study will be carried out with the participation of healthy individuals who do not suffer from a particular disease or pathological process. 4) in addition, the fermented milk to be used in the study is produced and sold commercially in our territory by the company YAKULT S/A Indústria e Comércio, Brazil, and is therefore widely available to the general population; Given this information, which highlights specific points involved in the study, if the use of fermented milk containing SCL proves to be effective at the end of the study, it can be used by any member of the control group by purchasing it commercially, without there being any obligation to make it available to the control group.

PENDENCY ATTENDED TO.

---

PENDENCY 9- In relation to the collection of blood, saliva and nasal swab, in addition to the information provided, the following information must be included in the project methodology (according to CNS Resolution 441/12 of May 2011):

9.a) and in what quantity (blood);

Answer 9a: As requested, the following text has been added to the project: "Blood will be collected in 4 tubes containing EDTA anticoagulants and in 1 tube without anticoagulants. It is worth noting that each tube can accommodate a volume of 4mL of blood, so we will not have a total volume of 20mL of blood from each volunteer on each occasion."

PENDENCY ATTENDED TO

9.b) which professional will carry out the collection and in which location; Answer 9b: As requested, the following text has been added to the project: "It is important to clarify not only that the collection of biological material will be carried out on the premises of the Santo Amaro University (UNISA) laboratory, under the responsibility of a nursing professional, trained and experienced to carry out this task (...)" PENDENCY ATTENDED TO

PENDENCY 9.c) under what conditions and in what form the biological material will be transported to the analysis laboratory; Answer 9c: As requested, the following text has been added to the draft: "(...) but also that all material collected will be kept refrigerated in a box.

**Address:** [name]

**Neighborhood:** VILA CLEMENTINO

**ZIP CODE:** 04.021-

**UF:** SP

**Municipalit:** SAO PAULO

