### **Collection of blood samples**

Blood samples will be collected in fasting condition, from an antecubital vein in tubes containing or not EDTA anticoagulants. After blood clotting or not, the tube will be centrifuged at 2500 rpm for 10min to obtain 500 µl of serum or plasma, which will be stored at -80°C for later use to determine circulating cells and serum/plasmatic parameters, as described below.

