### **Whole blood culture**

A volume of 100µL of the blood sample will be mixed with 900µL of culture medium, containing 10% fetal bovine serum + RPMI 1640, and will be incubated for 48 hours in 48 well plates, maintained in an air-conditioned oven with 95% oxygen and 5% carbon dioxide at

37°C. At the same time point, another well containing the same mixture of blood and medium will be submitted to stimulation with lipopolysaccharide (LPS) and maintained under the same conditions as previously reported. After the incubation period, the culture supernatant will be collected and centrifuged at 1400 rpm for 10 minutes, and a volume of, at least, 500µL will be frozen at 80°C for further evaluation of cytokine concentration.

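### As listed, the LPS whole-blood culture can only draw on EDTA blood, and its incubator gas reads 95% oxygen; a one-tube swap and a gas correction would protect this secondary outcome

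*Combined protocol and SAP*

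**What the plan says.** - **Tubes, protocol (Collection of blood samples).** Blood is taken "from an antecubital vein in tubes containing or not EDTA anticoagulants". No other anticoagulant is named.
- **Tubes, ethics committee opinion (answer to Pendency 9.a).** "Blood will be collected in 4 tubes containing EDTA anticoagulants and in 1 tube without anticoagulants". The same answer gives the volume: "each tube can accommodate a volume of 4mL of blood, so we will not have a total volume of 20mL of blood". The negative looks like a translation slip.
- **Culture (Whole blood culture).** A volume of 100 µL "of the blood sample will be mixed with" 900 µL of medium "containing 10% fetal bovine serum + RPMI 1640, and will be incubated for 48 hours in 48 well plates". The section does not say which tube supplies the blood and mentions neither a wash nor added calcium. A second well of the same mixture "will be submitted to stimulation with lipopolysaccharide (LPS) and maintained under the same conditions".
- **Gas (Whole blood culture).** The plates are kept in an "air-conditioned oven with 95% oxygen and 5% carbon dioxide".
- **Outcome (Determination of cytokine concentration).** Ten cytokines are measured in serum, in saliva and in the culture supernatant, the last with and without LPS.
- **Rank (Objectives).** Systemic immune and inflammatory responses are secondary. Salivary IgA is primary.
- **Contrast.** Blood cell count and Immune cell immunophenotyping each name EDTA tubes explicitly. Whole blood culture names none.

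**The concern.** Whole-blood culture with LPS is a functional assay: live leukocytes must respond over 48 hours. EDTA prevents clotting by binding calcium, on which leukocyte activation and cytokine secretion depend. If EDTA blood goes into the well unwashed, the chelator goes with it. An atmosphere that really was 95% oxygen would be a second departure from ordinary culture conditions. The plan gives no reason for either condition.

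At stake is the sensitivity of one part of the secondary objective. Ten cytokines under two conditions make 20 variables, each measured on five occasions. The Introduction cites findings from LPS-stimulated whole-blood culture in triathletes as part of the rationale, so this readout matters to the investigators. It also cannot be repaired later, because the cultures need fresh cells from draws tied to one race.

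**Working it through.** **1. The plan's own figure.** Tubes: 4 EDTA + 1 plain = 5. Volume: 5 × 4 mL = 20 mL, of which 16 mL is EDTA blood and 4 mL plain. The stated 20 mL is reproduced.

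**2. Which blood can be cultured.** The listed types are EDTA and no anticoagulant. The plain tube clots and yields serum. That leaves EDTA blood as the only listed anticoagulated blood. This is an inference by elimination from Collection of blood samples and the answer to Pendency 9.a.

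**3. Dilution.** 100 / (100 + 900) = 0.1, so whatever EDTA is in the blood is diluted tenfold in the well.

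**4. Calcium balance.** None of these concentrations is in the documents; all are assumptions:
- EDTA in a filled tube: 1.5-2.2 mg/mL of the dipotassium salt. Dividing by 404.5 g/mol gives 3.7-5.4 mM.
- Calcium: 0.42 mM in RPMI, 2.5-3.5 mM in fetal bovine serum, 2.2-2.6 mM in plasma.
- Plasma is 55% of blood volume, serum is 10% of the 900 µL, and EDTA binds calcium 1:1.

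EDTA in the well = 0.1 × (3.7 to 5.4) = 0.37 to 0.54 mM.

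Total calcium in the well = 0.81 × RPMI + 0.09 × serum + 0.1 × 0.55 × plasma:
- Low: 0.340 + 0.225 + 0.121 = 0.686 mM.
- High: 0.340 + 0.315 + 0.143 = 0.798 mM.

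| Case | EDTA (mM) | Calcium (mM) | Share bound | Left unbound (mM) |
|---|---|---|---|---|
| Least binding | 0.37 | 0.798 | 46% | 0.428 |
| Most binding | 0.54 | 0.686 | 79% | 0.146 |

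**5. Sensitivity to the assumptions.**
- With serum calcium at 3-4 mM and plasma at 2.3-2.5 mM, total calcium is 0.74-0.84 mM and the share bound is 44-74%.
- With serum calcium left out, total calcium is 0.461-0.483 mM and the share bound runs from 77% to 100%.
- A half-filled tube doubles EDTA in the well to 0.74-1.08 mM. Against 0.686-0.798 mM that is a ratio of 0.93 (0.74 / 0.798) to 1.57 (1.08 / 0.686), that is, near-complete to complete binding. The documents set no minimum fill.

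**6. Gas.** Taking air as about 21% oxygen (an assumption), 95 / 21 is about 4.5, so the stated gas is more than four times atmospheric oxygen.

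**7. Where the arithmetic stops.** No figure in the documents links bound calcium or oxygen level to cytokine release, so no effect size follows.

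**The case against.** The case on the other side has real weight.

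- **The tube is inferred.** Whole blood culture refers only to the blood sample. The 4 + 1 list may be incomplete, because it does not count the NKVUE tubes in Cytotoxicity Assay of NK cells. It also comes from an ethics reply describing a different version of the study (2024 race, 60-70 participants, symptoms as primary). This stands as a limit on certainty. But the current section on blood collection names the same two types, and no alternative is written anywhere.
- **Calcium is not exhausted.** In a filled tube with serum calcium counted, 0.146-0.428 mM stays unbound, and the upper end matches the 0.42 mM assumed for RPMI itself. This stands. Under-filling is a possibility, not something the documents report.
- **95% oxygen may mean 95% air.** The same section gives a freezing temperature of 80°C, where Saliva sample collection has -80°C, so slips occur. This is plausible. The text still needs correcting, since laboratory staff work from it.

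Three stronger readings are tempting, and the documents do not support them.

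- A reader might infer that the stimulated cytokine outcome is distorted. Nothing in the documents shows the direction or size of any effect.
- A reader might infer bias between LcS and placebo. The arms are randomised and blinded, and the LPS and control wells share the same conditions, so both arms are treated alike.
- A reader might extend the point to the NK interferon-gamma test. That test uses its own commercial tubes, and nothing says they are filled from EDTA tubes.

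**Conclusion.** The point holds as a cheap improvement. Followed as written, the plan cultures EDTA blood in 95% oxygen. On the assumed concentrations, roughly 45-80% of the calcium in the well would be bound with a filled tube and serum calcium counted, and more if the tube is under-filled or serum calcium is ignored. That may suppress or alter cytokine release and add variation between participants and occasions. The likely cost is reduced sensitivity and added noise in one of three cytokine matrices within a secondary objective, by an amount the documents do not allow anyone to calculate. The salivary IgA primary endpoint and its sample size are unaffected.

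The conclusion rests on the tube list being complete for the culture, and on chelator and calcium concentrations that are not in the documents.

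**What to change.** 1. In Collection of blood samples and Whole blood culture, name the anticoagulant for the culture and draw that blood into one heparin tube in place of one of the four EDTA tubes. The total stays at 5 × 4 mL = 20 mL. The two wells described need 2 × 100 µL = 0.2 mL, so one 4 mL tube is ample.
2. Keep EDTA for cell counts and immunophenotyping.
3. In Whole blood culture, correct the incubator gas to 95% air and 5% CO2.

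The cost is one tube type at each draw and a few changed sentences, submitted as an amendment as the ethics committee's Recommendation 1 requires. EDTA blood falls from 16 mL to 12 mL per occasion, and the laboratory should confirm that this is enough for its other uses. The change has to be in place before sampling starts.
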